10.16.2 Imputation of Diagnosis and Prior Disease History

The partial start date for initial diagnosis will be assigned to 15th day of the month (if only day is missing) or July 1st (if both month and day are missing).

For completely missing dates no imputation will be performed.

10.16.3 Missing Response Data

Patients with missing response data will be considered non-responders, unless specified otherwise.

10.16.4 Imputation of Laboratory Values with Character Symbol

Missing laboratory data will not be imputed. However, laboratory values of the form of "< x" (i.e., below the lower limit of quantification) or "> x" (i.e., above the upper limit of quantification) will be imputed as "x" for the purpose of calculation of summary statistics and comparing to normal ranges. These values will still be displayed as "< x" or "> x" in the listings.

10.17 Time Conversion

Time conversion will follow the rules described below:

- 1 week = 7 days,
- 1 month = 30.4375 days,
- 1 year = 365.25 days.

11.0 Interim Analyses

An analysis for futility will be performed when the sample size is considered enough for such analysis and for each indication, as described below in this section (for further details please refer to study protocol). Efficacy data and outputs will also be a part of the IDMC review.

The criteria for conclusion of futility, for each indication, are as follows:

- Indication 1 (Advanced and/or metastatic non-small cell lung cancer [NSCLC]):
 - N = 21 patients if the number of responses is less than 2 ($r < 2$)
- Indication 2 (Microsatellite instability-high [MSI-H] or mismatch repair deficient [dMMR] colorectal cancer):
 - N = 12 patients if the number of responses is less than 4 ($r < 4$)
- Indication 3 (Recurrent or metastatic cutaneous squamous cell carcinoma [cSCC]):
 - N = 12 patients if the number of responses is less than 4 ($r < 4$)
- Indication 4 (Advanced hepatocellular carcinoma):
 - N = 19 patients if the number of responses is less than 2 ($r < 2$)
- Indication 5 (Metastatic castration-resistant prostate cancer [mCRPC]):
 - N = 35 patients if the number of responses is less than 1 ($r < 1$)
- Indication 6 (Recurrent ovarian cancer):
 - N = 21 patients if the number of responses is less than 2 ($r < 2$)

For the purposes of interim analyses, in the case of ongoing patients with any unconfirmed response and for whom a confirmatory scan is still pending:

- Responders (PR, CR) or patients with SD that, at the time of the futility analysis, did not yet have a second (confirmatory) tumor assessment performed will be considered to have an Unconfirmed response (PR, CR) or Unconfirmed SD as BOR, respectively. Such BORs will be presented with "Unconfirmed" label.
- ORR will also include Unconfirmed PR and Unconfirmed CR in the numerator.

For the purpose of conducting the interim analysis, a temporary futility analysis population will be defined based on the patients which are deemed necessary for such interim analysis as described above. This population flag will be removed once all futility analyses have been performed.

12.0 Statistical Methods

All data collected during this study will be displayed in data listings on the largest population for which data is available, unless otherwise specified. Data listings will be sorted by indication and patient ID as a minimum, additional sorting variables will be specified as appropriate in the listing shell. Listings will include all relevant derived variables – those variables will be marked as "(derived)". Each listing will also contain a flag for the related population: for safety data, if the patient is in the ASaT population; for efficacy outputs, if the patient is in the efficacy and ASaT populations, etc. When listing options from the CRF in the case of 'Other: Specify', concatenate the specify text e.g. 'Other: XXXXXXXXXX'; in the case of missing end date due to an ongoing event, medication or procedure, the text 'ongoing' will be inserted in place of the end date.

Descriptive statistics (number of observations [n], mean, median, standard deviations [STD], minimum, Q1, Q3 [or interquartile range as indicated below], and maximum values) for continuous variables will be presented. Mean, median, Q1 and Q3 will be presented to 1 decimal more than original data. STD will be presented to 2 decimals more than original data. Minimum and maximum will match the decimal points in the original data. For categorical variables, summary measures will include the frequency and percentage (with 1 decimal place) of patients in each category. Percentages will not be displayed for zero counts.

Where appropriate the set of summary tables will be reported for each indication separately. Some outputs may be indication specific and only produced for that indication.

The analyses will be descriptive, no formal testing of statistical hypotheses is planned.

All data summaries and tabulations will be prepared with SAS® Version 9.4 or higher.

12.1 Patient Disposition

The number and percentage of patients and each population to which they belong will be presented, together with the reason for exclusion from each population.

The number and percentage of patients screened (and reason for screen failure), enrolled, and treated in the study will be presented, together with the:

- number and percentage of patients who discontinued from the study and a breakdown of the corresponding reasons for discontinuation
- number and percentage of patients who discontinued study treatment with the corresponding reasons.

Disposition will be summarized descriptively for all screened patients, overall for the study and for each indication separately.

The number of patients screened, enrolled, and treated by country and center will also be presented.

12.2 Demographic and Baseline Characteristics

Demographic and baseline characteristics data will be summarized descriptively for each indication separately for the ASaT population. Each summary will be repeated for the efficacy and per protocol populations.

12.2.1 Demographics

Demographic characteristics will be summarized using the following information from the Demographics CRF page: Sex, ethnicity, race, age at informed consent and age group. From other CRF pages also, baseline weight (kg), baseline height (m), baseline BSA (m²), baseline BMI (kg/m²) and baseline Eastern Cooperative Oncology Group (ECOG) status will be summarized.

12.2.2 Primary Disease History

Primary disease history will be listed and summarized using the information from the Cancer History CRF page. Variables to be summarized include location of primary tumor, time since diagnosis at ICF signature, stage of disease at diagnosis, and prior treatment with checkpoint inhibitors. The number of previous lines of systemic therapy will be summarized. Prior mutations and other genetic analysis data will be listed only.

12.3 Prior Therapy for Primary Diagnosis

A tabulation of prior systemic anti-cancer therapies coded according to WHO Drug dictionary (version March 22 B3 or later) will be presented in the Efficacy, ASaT and Per Protocol populations. Prior systemic anti-cancer therapies will be tabulated and categorized by medication group (ATC level 2) and preferred term using counts and percentages.

A tabulation of non-systemic anti-cancer therapies coded according to MedDRA (version 24.1 or later) will be presented for the Efficacy, ASaT and Per Protocol populations. Prior non-systemic anti-cancer therapies will be tabulated and categorized by System Organ Class and Preferred Term using counts. Systemic and non-systemic therapies will be presented separately. Radiation therapy is not coded and will be listed only.

Full details of prior systemic anti-cancer therapies will be listed only.

12.4 Medical History

Medical history will be coded according to Medical Dictionary for Regulatory Activities (MedDRA, Version 24.1 or later).

Medical history will be tabulated by system organ class (SOC) and preferred term (PT) using counts and percentages for the ASaT population.

12.5 Treatments

12.5.1 Exposure to Study Treatments

Descriptive statistics will be provided for the duration of exposure (days), the total number of cycles started, the total number of doses administered, number of patients with at least one dose adjustment (SOT101 only), cumulative dose, actual dose intensity and relative dose intensity on each study treatment. Summaries will be performed on the ASaT, efficacy and per protocol populations. Compliance per protocol will be listed only. Relative Dose Intensity by cycle will be plotted per patient using box plots overlaid with a mean profile line, and only presented for cycles with at least 20 patients data available.

The total number of doses administered will be summarized as well as the frequency of patients with 1, 2, 3, 4, 5, 6, 7, 8, or ≥ 9 injections.

Information regarding patients' dosing regimens, including total volume administered and dose adjustments, will be listed only.

12.5.2 Prior and Concomitant Medications, and Procedures

Medications received priorly and concomitantly with study drug, categorized by medication group (ATC level 2) and preferred term according to WHODrug (Latest Version), will be summarized for the ASaT population.

Prior and concomitant procedures will be coded according to MedDRA and summarized by System Organ Class and Preferred Term.

Prior and concomitant medications and procedures will be tabulated separately using counts and percentages to display the number and percentage of patients using at least one medication.

Full detail of medications and procedures will be presented in listings only.

12.6 Protocol Deviations

Protocol deviations will be documented by category (as per the latest study Protocol Deviation Guidance document). All deviations will be reviewed, categorized, designated important or not important, and finalized prior to database lock. Important protocol deviations will be defined as those potentially impacting safety or efficacy assessments and analyses. Additional details of what will be considered important protocol deviation can be found in the Protocol Deviation Guidance document.

Important protocol deviations for patients in the enrolled population will be summarized by deviation category. All protocol deviations will be listed only.

Any COVID-19-specific protocol deviations will be listed separately.

12.7 Efficacy Analyses

All efficacy analyses will be summarized descriptively for each indication separately on the efficacy population, the ASaT population, and the Per protocol population where applicable.

Subgroup analyses may be performed on selected populations and efficacy endpoints. These will include the subgroups of CPI naïve vs. CPI pre-treated, patients with higher risk factors such as ECOG ≥ 2 vs. ECOG < 2 , or more than 2 previous lines of therapy.

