- Cemiplimab was investigated in a single-arm, multicenter trial (NCT02760498) in 78 patients with locally advanced cSCC for whom there was no widely accepted standard of care. In this trial, cemiplimab showed antitumor activity and an acceptable safety profile.
- Patients treated with nanrilkefusp alfa showed responses in study SC103 (AURELIO-03) after resistance to or failure on immune checkpoint inhibitors.
- This indication is therefore chosen to test the ability of the combination of nanrilkefusp alfa and pembrolizumab to improve pembrolizumab efficacy while maintaining safety as first-line treatment (based on data from KEYNOTE-629) and as second-line treatment if refractory or relapsed after an immune checkpoint inhibitor-containing regimen (based on data from study SC103 [AURELIO-03]).
- Advanced hepatocellular carcinoma after recurrence or failure of an immune checkpoint inhibitor (not applicable in France)
  - Pembrolizumab was investigated in KEYNOTE-224 (NCT02702414), a single-arm, multicenter trial in 156 patients with hepatocellular carcinoma who had disease progression on or after sorafenib or who had not received prior systemic therapy. In this trial, pembrolizumab was effective and tolerable in patients who had previously been treated with sorafenib. First-line pembrolizumab monotherapy provided durable antitumor activity and promising OS.
  - The combination of atezolizumab and bevacizumab was investigated in IMbrave150 (NCT03434379), a randomized, multicenter, open-label trial in 558 patients with unresectable hepatocellular carcinoma who had not previously received systemic treatment. Atezolizumab plus bevacizumab resulted in better outcomes than sorafenib.
  - This indication is therefore chosen to investigate the combination of nanrilkefusp alfa and pembrolizumab as second- to fourth-line treatment in patients who have received immune checkpoint inhibitor therapy.
- Treatment-refractory mCRPC after recurrence or failure of docetaxel and prior treatment with abiraterone, enzalutamide, or any other androgen receptor-targeted agent

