#### Disease characteristics

4. Patients with the following histologically or cytologically confirmed solid tumor indications and line of treatment:
  - NSCLC
    - For the second-line or third-line treatment of patients with advanced and/or metastatic NSCLC with disease progression on or after an immune checkpoint inhibitor-containing regimen and a platinum-containing regimen, with no EGFR or ALK genomic tumor aberrations, and who are not amenable to curative treatment
  - Colorectal cancer
    - For the first-line treatment of patients with unresectable or metastatic MSI-H/dMMR colorectal cancer
  - cSCC
    - For the first-line treatment of patients with recurrent or metastatic cSCC or second line if refractory or relapsed after an immune checkpoint inhibitor-containing regimen, and in whom radiotherapy is not feasible (based on data from study SC103 [AURELIO-03])
  - Advanced hepatocellular carcinoma (not applicable in France)
    - For the second- to fourth-line treatment of patients with advanced hepatocellular carcinoma having progressed on or after a checkpoint inhibitor-containing regimen
  - mCRPC
    - For the second- to fifth-line treatment of patients with mCRPC after recurrence or failure of docetaxel and prior treatment with abiraterone, enzalutamide, or any other androgen receptor-targeted agent
  - Ovarian cancer
    - For the second- to fifth-line treatment of patients with advanced ovarian cancer after recurrence or failure on the last platinum-based therapy within 6 months
5. Have measurable disease per RECIST 1.1 as assessed by the local site investigator/radiology; lesions situated in a previously irradiated area are considered measurable if progression has been demonstrated in such lesions

mCRPC: Patients with both measurable and non-measurable disease will be enrolled. At least 35 patients with measurable disease will be enrolled. Patients with no measurable disease and only widespread bone disease must have a CTC count of  $\geq 5$  cells per 7.5 mL of blood.

6. Availability of tumor tissue from a fresh biopsy at screening unless the biopsy cannot be obtained due to safety reasons or non-accessibility of the tumor site. If it is not possible to obtain a fresh biopsy, every effort should be taken to retrieve an archival biopsy. Archived, fixed tumor tissue may only be collected if taken preferentially after completion of the most recent systemic tumor therapy and within 12 months prior to the first dose of study treatment.

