7. Performance status: Eastern Cooperative Oncology Group (ECOG) performance score 0-1
8. Must have recovered from all AEs (except alopecia) due to previous therapies to grade  $\leq 1$  toxicity (excluding alopecia) or have stable grade 2 neuropathy

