### **9.3.2 Primary endpoint analysis**

The ORR is defined as the proportion of patients with CR or partial response (PR). ORR will be analyzed and presented as a point estimate and a 95% CI for each indication separately. Patients with missing data will be considered as non-responders.

Sensitivity analyses will include the use of:

- ASaT and PP populations
- No imputation of missing data

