8.0 Study Design

This is a phase 2, open-label, single-arm, multicenter study of SOT101 in combination with pembrolizumab to evaluate the efficacy and safety in patients with selected advanced/refractory solid tumors.

Participation of each patient will consist of the Screening, Treatment, and Follow-up study periods.

Eligible patients will be treated in cohorts by the following histologically or cytologically confirmed solid tumor indications, line of treatment.

- Non-small cell lung cancer (NSCLC)
 - For the second-line or third-line treatment of patients with advanced and/or metastatic NSCLC with disease progression on or after an immune checkpoint inhibitor-containing regimen and/or a platinum-containing regimen, with no epidermal growth factor receptor (EGFR) or anaplastic lymphoma kinase (ALK) genomic tumor aberrations
- Colorectal cancer
 - For the first-line treatment of patients with unresectable or metastatic Microsatellite Instability-High/Mismatch Repair Deficient (MSI-H/dMMR) colorectal cancer
- Cutaneous squamous cell carcinoma (cSCC)
 - For the first-line treatment of patients with recurrent or metastatic cSCC or second-line if refractory or relapsed after an immune checkpoint inhibitor-containing regimen (based on data from study SC103)
- Advanced hepatocellular carcinoma
 - For the second-line or later-line treatment of patients with advanced hepatocellular carcinoma having progressed on or after a checkpoint inhibitor-containing regimen
- Metastatic castration-resistant prostate cancer (mCRPC)
 - For the second-line or later-line treatment of patients with mCRPC after recurrence or failure of docetaxel
- Ovarian cancer
 - For the second-line or later-line treatment of patients with advanced ovarian cancer after recurrence or failure on platinum-based therapy within 6 months

During the treatment period, patients will be treated with SOT101 together with pembrolizumab until any of the criteria for treatment discontinuation is met.

Patients will be treated with SOT101 12 µg/kg subcutaneously on day 1 (± 1 day for the cycle start), day 2, day 8, and day 9 in combination with pembrolizumab 200 mg intravenously (IV) on day 1 in 3-week cycles after all procedures and assessments have been completed.

Pembrolizumab will be administered as an IV infusion via peripheral or central venous line starting within 30 minutes after the first dose (day 1) of SOT101 in each 3-week cycle.

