12.7.1 Objective Disease Response

Descriptive statistics (frequency and percentage) for ORR and iORR, and the two-sided exact 95% Clopper-Pearson confidence interval⁽⁴⁾ (CI) for the iORR/ORR will be presented for patients with measurable disease in each indication separately. Primarily, patients with missing data will be considered to be non-responders.

Sensitivity analyses on iORR and ORR will be performed including the use of:

- ASaT and PP populations
- No imputation of missing data (i.e. only patients with evaluable post-baseline tumor assessment)

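### Must the SAP guarantee a cutaneous squamous cell carcinoma response rate split by prior checkpoint inhibitor treatment?

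*SAP*

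**What the plan says.** Inclusion criterion 4 in Protocol 5.1 defines the cSCC cohort as: "For the first-line treatment of patients with recurrent or metastatic cSCC or second line if refractory or relapsed after an immune checkpoint inhibitor-containing regimen". SAP 8.0 repeats it: "For the first-line treatment of patients with recurrent or metastatic cSCC or second-line if refractory or relapsed after an immune checkpoint inhibitor-containing regimen". Protocol 4.2 explains the choice by citing separate evidence for each setting. It wants to test the combination "as first-line treatment (based on data from KEYNOTE-629) and as second-line treatment if refractory or relapsed after an immune checkpoint inhibitor-containing regimen", with study SC103 as the support for the second part.

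The primary output is set per indication. Protocol 9.3.2 says "ORR will be analyzed and presented as a point estimate and a 95% CI for each indication separately". SAP 12.7.1 says ORR and iORR "will be presented for patients with measurable disease in each indication separately". The sensitivity analyses there change the population (all-subjects-as-treated, per protocol) or the missing-data rule, so they pool the two settings as well.

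SAP 12.7 covers subgroups in two sentences. The first is permissive: "Subgroup analyses may be performed on selected populations and efficacy endpoints". The second states, in the future tense and without qualification, which subgroups are included. It starts with CPI-naive against "CPI pre-treated, patients with higher risk factors such as ECOG" of 2 or more, then adds more than two previous lines. Neither sentence names an indication or an endpoint.

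**The concern.** A pooled ORR in a mixed cohort depends on who was accrued as well as on what the drug does. If patients who have already failed a checkpoint inhibitor respond less often, a good first-line result could be diluted, and the reader could not tell this from the pooled figure. The baseline table shows the mix but not which patients responded.

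The subgroup list also looks generic when applied to cSCC. Criterion 7 admits only "Eastern Cooperative Oncology Group (ECOG) performance score 0-1", so the ECOG contrast has an empty side. The cohort takes first- and second-line patients only, so more than two previous lines should not occur either. Barring eligibility deviations, CPI history is the only one of the three named contrasts with patients on both sides in cSCC, and it sits under a permissive verb. With an optional split in an open-label trial, a sponsor could decide whether to show it after seeing the results.

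**Working it through.** **1. The plan's own cSCC figures.** Inputs: N = 57; benchmark, minimal and desired ORR 44%, 54.1% and 62.5%; uniform prior (Protocol 9.4 and 9.5). Desired responses are 57 × 0.625 = 35.6. The posterior is Beta(1 + x, 1 + 57 − x), and P(ORR > 54.1%) is 0.861 at x = 35, 0.895 at x = 35.6 and 0.912 at x = 36. All meet the stated 80%. For the futility rule (fewer than 4 of 12), the 80% exact upper limit is 47.5% at 3/12, which excludes 54.1%, and 55.9% at 4/12, which includes it. Both figures reproduce, and neither uses a split by CPI history.

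**2. What the pooled rate and the mix leave open.** With R responders among N patients, m of them pre-treated, the CPI-naive responders lie between max(0, R − m) and min(N − m, R). Take R = 30, N = 57, m = 14 as an illustration:

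- lower bound 30 − 14 = 16, so 16/43 = 37.2% (all 14 pre-treated respond);
- upper bound min(43, 30) = 30, so 30/43 = 69.8% (none of the 14 respond).

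For R = 6, N = 12, m = 3, the range is 3/9 = 33.3% to 6/9 = 66.7%. So the two summary tables together do not give the two rates. The listings do.

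**3. How far the blend can move.** The documents give no post-CPI response rate for cSCC and no expected share, so both are assumptions. Let the CPI-naive ORR be 62.5% and the post-CPI ORR be p. The pooled true ORR falls below t when the pre-treated share exceeds (0.625 − t)/(0.625 − p).

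| Assumed p | Share for t = 54.1% | Share for t = 44% |
|---|---|---|
| 15% | 0.084/0.475 = 17.7% | 0.185/0.475 = 38.9% |
| 30.6% | 0.084/0.319 = 26.3% | 0.185/0.319 = 58.0% |
| 44% | 0.084/0.185 = 45.4% | never below |

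The final ORR is not compared with either value. The table shows dilution, not a wrong decision.

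**4. Effect on the interim rule.** The number of responders among 12 is the sum of Bin(12 − m, 0.625) and Bin(m, p). P(fewer than 4) is 0.95% with m = 0. Over the three values of p it is 1.6% to 3.0% with m = 2, 2.1% to 5.1% with m = 3, and 4.3% to 21.6% with m = 6. It stays modest unless about half of the first 12 are pre-treated and their response rate is low.

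**5. What a guaranteed table would show.** Exact 95% Clopper-Pearson intervals:

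| Responders/N | ORR | 95% CI |
|---|---|---|
| 30/57 (pooled) | 52.6% | 39.0% to 66.0% |
| 27/43 (CPI-naive) | 62.8% | 46.7% to 77.0% |
| 3/14 (pre-treated) | 21.4% | 4.7% to 50.8% |
| 6/9 | 66.7% | 29.9% to 92.5% |
| 1/3 | 33.3% | 0.8% to 90.6% |

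SAP 6.1 records that recruitment stopped after the August 2023 futility analysis. The documents do not give the cSCC count reached, so the last two rows may be closer to reality than the first three.

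**6. Where the split would apply.** Under criterion 4, NSCLC and hepatocellular carcinoma require prior CPI treatment, and colorectal cancer is first line. The prostate and ovarian criteria do not mention it. cSCC is the only indication whose criteria name both CPI settings. An analyst reading SAP 12.7 has little doubt where this contrast belongs.

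**The case for a change.** The best case for a change is that it costs one sentence and one table from data already collected, and that a permissive verb leaves production of the split open to choice. On a strict reading, the second sentence of SAP 12.7 only says which subgroups are used if any are run. The documents therefore contain no unconditional commitment to a cSCC ORR by CPI history. That reading is fair, and the arithmetic in steps 2 and 3 is sound.

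It does not carry the point further, for four reasons. The contrast is already named in the SAP, so showing it would not be a post hoc invention. The rationale in Protocol 4.2 gives reasons for choosing one indication and sets no separate objectives. Protocol 9.1 asks for an ORR per indication or disease cohort, without hypothesis testing, and the pooled ORR supplies that. The information will be available: SAP 12.2 and 12.2.2 summarise prior CPI treatment by indication, SAP 12.0 lists all data by indication and patient, and SAP 12.7.2 plans patient-level plots. Finally, this SAP version already reports the futility analysis, so making the table mandatory in it would also follow sight of some response data, although it would still precede database lock.

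**Conclusion.** No change follows. This is a gap in detail that analysts can be expected to fill sensibly: the split is named, the variable is collected and summarised, and eligibility points to cSCC. Two adjacent sentences in SAP 12.7 differ in firmness, and no number, decision rule or primary estimate depends on which is followed. The pooled cSCC ORR is a valid answer to the per-indication objective, provided it is read as an average over the accrued mix.

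The size of the issue is limited on the reporting side too. The pooled rate and the mix can leave the CPI-naive ORR open over a wide range (37.2% to 69.8% in the example), but cross-tabulating two listings closes that range. The split rates would carry wide intervals at the planned 57 patients and wider ones in a cohort cut short. The dilution figures rest on assumed post-CPI rates of 15% to 44%, for which the documents have no cSCC source. The conclusion does not depend on them.
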